### 3.2. Secondary Outcomes

1. IL-25 transcript expression in nasal scraping samples obtained on days 1, 2, and 7 (as compared to day 0).
2. Expression by nasal epithelial cells of a type 2 cytokine-inducing profile will be determined by also evaluating the time course of IL-33 and TSLP transcript expression by qPCR on nasal scraping samples obtained on days 0, 1, 2, 3, 4 and 7.
3. Expression of this type 2 cytokine-inducing profile will be corroborated by evaluating IL-25, IL-33, and TSLP protein expression by EIA on nasal secretion samples obtained via immunosorbent sponge.
4. Airway inflammation will be determined as increases in circulating absolute eosinophil counts, increased FeNO, and as changes in methacholine PD20.
5. Severity of RV infection will be corroborated as increases in upper respiratory symptoms using modified Jackson scores (1). This scoring system includes sneezing, nasal discharge, nasal obstruction, sore throat, headache, malaise, and chills.
6. Severity of RV infection will be correlated with decreased innate immunity as assessed as reduced IFN- $\alpha$ , - $\beta$ , - $\lambda$ , and IL-15 measured as qPCR of nasal scrapings and as enzyme immunoassays (EIAs) of nasal secretions (sponge-derived samples).

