All subjects in the proposed study will be inoculated with RV-16 and monitored daily for 4 days following inoculation in the clinical research center at UVA hospital and again on day 7 dpi. Daily monitoring will include upper and lower respiratory symptoms scores, and FEV1 measurements (using a hand held FEV1 monitor given to each subject), which will be recorded twice daily (morning and evening) on diary cards. Subjects will also be recording the number of puffs of albuterol used daily from metered dose inhalers. In addition, monitoring each morning will include a physical examination focused on the respiratory tract, along with spirometry and measurements of expired nitric oxide (FeNO). This monitoring will be done to enhance our ability to detect changes during the acute infection and to ensure safety. The research team member will be a licensed physician or nurse and will be readily available should any problems occur. Thus far, no significant problems or serious adverse events have occurred for any of the asthmatics inoculated with either RV-16 or RV-39. The inclusion of mild-/moderate-persistent asthmatics who are very well controlled on inhaled CCS could lead to more severe exacerbations. However, this has not been the experience of other research groups enrolling this population (58). Furthermore, as noted, the average American has 4 respiratory infections/yr and we would argue that as none of these subjects will have had even a modest asthma exacerbation in the previous 3 years (over which time they will on average have had 12 RV infections) we do not feel this modification adds an untoward risk to the study. And that the current safety monitoring criteria will continue to suffice.

As for any adverse long-term safety effects of an experimental RV-16 infection, the cold symptoms observed have been generally similar to, but a bit shorter in duration than a natural RV infection (see above). Because most adults will

experience at least one or two viral induced colds a year, it would be very difficult to differentiate any adverse effects of an RV-16 experimental infection from the effects of a subsequent natural respiratory tract infection in an effort to evaluate any safety problems long-term.

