### **Study Visit 3, 4, and 5 (Day 1, 2, and 3)**

1. Diary cards will be reviewed for symptom control and AEs.
2. A limited physical examination will be performed including chest auscultation and temperature
3. Nasal scraping
4. Nasal wash / sponge
5. Spirometry
6. Exhaled nitric oxide (FeNO) on asthmatics only

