## 13. Statistical Considerations and Analytical Plan

### 13.1 Overview

**Objectives:** Our primary objective will be to address the hypothesis that epigenetic changes selectively develop in nasal epithelial cells (EC) during the evolution of allergic airway disease as a result of which nasal EC are programmed to produce cytokines central to orchestrating an allergic inflammatory immune response in the upper – and lower – airways. We will determine whether nasal epithelium from allergic asthmatics and rhinitics when infected with RV, is programmed to secrete cytokines that promote a Th2 cytokine “signature” (IL-25, IL-33, and TSLP) as well as mediators directly driving engagement of an allergic inflammatory process (including CCL5, CCL11, CXCL1, and GMCSF). A total of 60 subjects will be enrolled including 20 each that are normal controls, allergic rhinitis controls, and asthmatics. Cytokine/chemokine will be collected at day 0, 1, 2, 3, 4, and 7 post-infection and evaluated by qPCR and EIA.

We will correlate the expression of these cytokines with engagement of an allergic inflammatory response, including eosinophil co-recruitment at days 1-4. In addition, we predict that in asthma and AR systemic increases in eosinophilia will be observed, but that only in asthmatics will increased asthma symptoms, bronchial hyperreactivity, and eNO be observed.

**Analytical approach:** The RV challenge model is an example of a serial study design, in which subjects will receive a nasal presentation of RV-16 on challenge day 0 and then they will be serially monitored in the CRU for 7 days. **Analytical method selection:** Due to the fact that most of our data collection will be serial in nature, i.e. data will be collected on challenge days 0, 1, 2, 3, 4, and 7, the analytical methods that we select to use to analyze our primary and secondary outcome data will take into account the *repeated measure* aspect of the RV challenge model. **Missing data:** We will make a concrete effort to limit the occurrence of missing data, and if deemed necessary, multiple-imputation methods will be utilized to control biases associated with incomplete data. **Levels of detection:** If specimen levels are below the level of assay detection, we will use the mid-point between 0 and the minimum detection level of the assay as the unit of analysis.

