**Units of analysis:** The day 0  $\log_e$ (IL-25 qPCR expression) measurements will be subtracted from the post-challenge day 1, 2, 3, 4, and 7  $\log_e$ (IL-25 qPCR expression) measurements and these *subject-specific* pre- versus post-challenge changes in  $\log_e$ (IL-25 qPCR expression) will be the units of analysis. **Analytical approach:** The changes in  $\log_e$ (IL-25 qPCR expression) on post-challenge days 1, 2, 3, 4, and 7 will be analyzed as repeated measures by way of a linear mixed model (LMM). **LMM fixed effects:** Two sources of variability in the pre- versus post-challenge changes in  $\log_e$ (IL-25 qPCR expression) will be of primary interest. One source of variability will be the study-group to study-group variability (i.e. asthmatics, allergic rhinitis controls, and healthy-controls) in the changes in  $\log_e$ (IL-25 qPCR expression), while the other source of variability will be the post-challenge day to day variability in the changes in  $\log_e$ (IL-25 qPCR expression). **Concomitant variable variability:** Variability in the  $\log_e$ (IL-25 qPCR expression) changes due to inherent differences in day 0  $\log_e$ (IL-25 qPCR expression) will be extracted from the residual error to increase statistical power. **Random effects:** *Subject-specific* and *time-specific* random effects will be incorporated into the LMM to allow *intra-subject* measurement correlation to be accounted for in variance estimation and hypothesis testing. **Hypothesis testing:** *Between-study-group comparisons:* With regard to hypothesis testing, the pivotal comparisons will be the *between* study-group comparisons of the mean changes in  $\log_e$ (IL-25 qPCR expression) on post-challenge study days 3 and 4 when cold symptoms are expected to peak. More specifically, we will compare if the study-day 3 and study-day 4 mean changes in  $\log_e$ (IL-25 qPCR expression) differ between the 3 different underlying study-populations after taking into account the inherent variability in challenge study-day 0  $\log_e$ (IL-25 qPCR expression). These comparisons will require conducting a total of 6 hypothesis tests (i.e. 3 per study day), and in order to maintain an *intraday* experimental-type I error rate of 0.05, the null hypothesis rejection rule for the “*intraday*” *between-group* comparisons will be based on a Bonferroni corrected two-sided  $p \leq 0.0167$  (i.e.  $0.05/3$ ) rejection rule. *Within-study-group comparisons:* On a per *study-group* basis, we will conduct statistical tests to determine if the means of the  $\log_e$ (IL-25 qPCR expression) distributions on post-challenge days 1, 2, 3, 4, and 7, differ from the mean of the  $\log_e$ (cytokine expression) distribution on challenge study day 0. The *within-study-group* comparisons will be considered *secondary* in nature, and this set of comparisons will be primarily focused on the challenge study-day 3 and challenge study-day 4 changes in mean  $\log_e$ (IL-25 qPCR expression) when symptoms are expected to peak. More specifically, we will test if the mean of the  $\log_e$ (IL-25 qPCR expression) distribution is the same on challenge study-day 0 and challenge study-day 3 and if the mean of the  $\log_e$ (IL-25 qPCR expression) distribution is the same on challenge study-day 0 and challenge study-day 4. A Bonferroni corrected two-sided  $p \leq 0.025$  (i.e.  $0.05/2$ ) decision rule will be utilized as the null hypothesis rejection criterion for this set of tests. **Confidence intervals:** To aid in data interpretation, a 95% confidence interval will be constructed for each *between-group* comparison and for each *within-group* comparison. **Scale of interpretation:** The point-estimate and the lower and the upper 95% confidence interval limits will be anti-log transformed so that point-estimate and the lower and the upper limits of the 95% confidence interval represent ratios of geometric mean cytokine expression. **Alternative analytical approach:** If the linear mixed model assumptions are deemed to be violated for this endpoint, we will use a linear mixed model based permutation test strategy to derive empirical based *distribution free* tests for testing the aforementioned *between-group* and *within-group* hypotheses.

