
**Analysis of FeNO:** FeNO will be derived from lung-function tests that will be conducted on challenge study days 0, 1, 2, 3, 4, and 7. **Data transformation:** If the FeNO measurement distributions for challenge study days 0, 1, 2, 3, 4, and 7 are positively skewed, the FeNO data will be transformed to the natural logarithmic scale, otherwise the FeNO data will be analyzed on the ppb scale. **Analytical approach:** The FeNO data will be analyzed via a LMM. **LMM specification:** The LMM specification will an exactly the same as the LMM model specification for the FEV1 analysis (see above). **Hypothesis testing:** The pivotal *between-group* comparisons will be focused on the post-challenge day 3 and day 4 changes in FeNO when symptoms are expected to peak. Baseline adjusted post-challenge day 3 and day 4 mean changes in FeNO will be compared in a pairwise manner between the 3 different study-populations.

In order to maintain an *intraday specific* experimental type I error rate 0.05, a Bonferroni corrected two-sided  $p \leq 0.05/3$  decision rule will be utilized as the null hypothesis rejection rule for this set of tests. Post-challenge day 1, 2, and 7 *between-group* comparisons of the changes in FeNO will be considered as secondary comparisons, and the same hypothesis testing procedures will be employed to conduct these *between-group* comparisons. *Within-group* related hypotheses will also be considered as secondary hypotheses.

***Analysis of bronchial hyperreactivity (methacholine PD20):*** The changes in bronchial hyperactivity from before challenge to after challenge will be quantified in terms of the changes in methacholine challenge PD20 from pre-challenge day -7 to post challenge day 4 ( $\Delta$  PD20). ***Analytical approach:*** The  $\Delta$  PD20 data will be analyzed by way of analysis of variance (ANOVA). ***Model specification:*** The primary source of  $\Delta$  PD20 variation that will be examined will be the variation due to study-group to study-group variation. ***Hypothesis testing:*** We will test if the 3 underlying study-population  $\Delta$  PD20 distributions share the same mean. If rejected a Bonferroni corrected two-sided  $p \leq 0.05/3$  decision rule will be utilized as the null hypothesis rejection rule for between-group comparisons. ***Alternative analytical approach:*** If the ANOVA model assumptions are violated, the  $\Delta$  PD20 data will be analyzed by *distribution-free* permutation methods.

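### Section 8 limits FeNO to asthmatics while Table I, 3.1 and 5.1 do not; if Section 8 governs, the three-cohort FeNO comparisons in 13.4.4 cannot be done

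*Combined protocol and SAP*

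**What the plan says.** **The analysis.** FeNO is one of three measures in secondary outcome 4 (Section 3.2): "Airway inflammation will be determined as increases in circulating absolute eosinophil counts, increased FeNO, and as changes in methacholine PD20". Section 13.4.4 gives FeNO the same linear mixed model as FEV1, with study group, post-challenge day, the day 0 value as covariate, and subject and time random effects. Its main hypothesis tests are between groups: day 3 and day 4 "mean changes in FeNO will be compared in a pairwise manner between the 3 different study-populations", each pair judged at two-sided p ≤ 0.05/3 within a day. Between-group comparisons on days 1, 2 and 7, and within-group hypotheses, are secondary. Section 13.1 predicts that "only in asthmatics will increased asthma symptoms, bronchial hyperreactivity, and eNO be observed".

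**Collection, Section 8.** The list for days 1 to 3 reads "Exhaled nitric oxide (FeNO) on asthmatics only". The lists for Visit 1 (day -7), Visit 2 (day 0), Visit 6 (day 4) and Visit 7 (day 7) carry the same limit, and Visit 8 (day 14) has it in parentheses.

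**Collection, elsewhere.** The Section 3.1 text schedules FeNO on days 0, 1, 2, 3, 4 and 7 without naming a cohort. The combined FEV1 and FeNO row of Table I is marked from day -7 to day 14, also without a cohort limit. Section 5.1 describes the monitoring of all subjects and includes FeNO in each morning's assessment: "along with spirometry and measurements of expired nitric oxide (FeNO".

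**The concern.** A comparison of three cohorts needs data from three cohorts. The Section 8 lists are what staff work from at each visit, and the same restriction in six separate lists does not look like a slip. If it is followed, two of the three cohorts have neither a day 0 baseline nor any post-challenge FeNO value.

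The scientific stake is specific. Sections 1.1 and 4.1 explain that the allergic rhinitis cohort is there to show that lower airway inflammation rises only in asthmatics. Of the three measures in secondary outcome 4, eosinophil count and PD20 are compared only from day -7 to day 4, so FeNO is the only one followed serially. A rise in asthmatics alone, with nothing measured in the other cohorts, cannot show that the rise is confined to asthmatics. FeNO not measured on days 0 to 7 cannot be recovered later.

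**Working it through.** **Inputs.** 20 subjects in each of 3 cohorts, 60 in all (Section 3.1); post-challenge days 1, 2, 3, 4 and 7, main days 3 and 4, 3 pairwise comparisons per day (13.4.4). The plan gives no FeNO standard deviation, sample size or power.

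**1. The plan's own threshold.** 0.05/3 = 0.0167, the decimal that 13.4.2 gives for the same rule on IL-25. It reproduces, and it is a correction for three between-group tests per day, so the three-cohort wording is deliberate. Where the plan means asthmatics alone, as for albuterol use in 13.4.4, it says so.

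**2. Counts if Section 8 governs.**
- Subjects without FeNO: 2 × 20 = 40 of 60 (67%).
- Main between-group comparisons: 3 pairs × 2 days = 6.
- Secondary between-group comparisons: 3 pairs × 3 days = 9.
- Each of the 15 pairs involves at least one cohort with no data.

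**3. Estimability.** Write the fixed part of the model as one mean per group and day plus a centred baseline covariate: 3 × 5 + 1 = 16 parameters. A contrast is estimable if it lies in the row space of the design matrix.

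| FeNO collected in | n (asthma / AR / healthy) | Design rank | Between-group contrasts, days 3 and 4 | Within-group changes, days 3 and 4 |
|---|---|---|---|---|
| Asthmatics only (Section 8) | 20 / 0 / 0 | 6 of 16 | 0 of 6 | 2 of 6 |
| All cohorts (3.1, Table I, 5.1) | 20 / 20 / 20 | 16 of 16 | 6 of 6 | 6 of 6 |

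The rank of 6 is the five asthma day means plus the covariate. The two within-group changes that survive are those of the asthma cohort.

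**4. Imputation.** Section 13.1 allows multiple imputation if needed. It cannot help here: with no observed FeNO in either control cohort, any imputed group difference would come from the imputation assumptions and not from data.

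**5. What the comparison offers if all cohorts are measured.** For one two-sample comparison with n = 20 per group, two-sided α = 0.05/3 and 80% power, the smallest detectable standardized difference is, by normal approximation, (2.394 + 0.842) × √(2/20) = 1.02 SD. With the noncentral t it is about 1.06 SD. Without a FeNO standard deviation this cannot be put in ppb. The same t calculation gives 1.136 against the 1.14 of Table II and 25.4 against the 25 of Table III, so the method agrees with the plan's own, although neither table concerns FeNO.

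**The case against.** The strongest reply is that Table I is the study schedule and that it, the Section 3.1 text and Section 5.1 all fit the three-cohort analysis. On that reading all 6 main comparisons can be run and the fault lies in the visit lists. This stands as far as it goes: the documents do not say which text governs or what was actually collected, so every loss counted above is conditional on Section 8. It does not remove the contradiction, because both sets of passages cannot be followed.

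Three stronger readings are tempting, and the documents do not support them.

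- *That the control cohorts have no FeNO data.* This is not established, for the reason just given.
- *That a secondary endpoint cannot be analysed.* FeNO is one of three measures in secondary outcome 4. The matching secondary objective 4 is worded for the asthma cohort. Section 13.4.4 already plans within-group FeNO hypotheses, and 13.6 defines within-group tests for every secondary outcome. Those remain possible in asthmatics under Section 8.
- *That the whole prediction in 13.1 loses its comparator.* It also covers asthma symptoms and bronchial hyperreactivity. Symptom assessment and methacholine challenge have no asthmatic-only limit in Table I or the visit lists. Only the exhaled nitric oxide part is exposed.

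It is also fair to say that no primary endpoint, power calculation or primary error-rate rule rests on FeNO.

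**Conclusion.** The concern holds as an internal contradiction with a conditional consequence. Section 8 confines FeNO to asthmatics at every visit that lists it; Section 3.1, Table I and Section 5.1 do not. If Section 8 governs, all 6 main and all 9 secondary between-group FeNO comparisons in 13.4.4 are lost, and the exhaled nitric oxide part of the prediction in 13.1 cannot be tested. If the other passages govern, none is lost. Change from day 0 within asthmatics is analysable either way.

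The counts assume the planned 20 subjects per cohort and literal adherence to one set of passages; partial collection in the control cohorts would fall between the two. Since one measure of one secondary endpoint is affected and no primary endpoint is, this should be fixed but does not threaten the main conclusions.

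**What to change.** Reconcile the passages before analysis, and record how many subjects in each cohort have FeNO at day 0 and at each later day.

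- **If the three-cohort comparison is wanted and FeNO is collected in everyone:** delete the asthmatic-only limit from the Section 8 lists for Visits 1 to 8, so that they match 3.1, Table I and 5.1. Section 13.4.4 then stands as written. The cost is a protocol edit and, wherever it has not been done, a short non-invasive breath test at visits that subjects already attend.
- **If FeNO is in fact collected only in asthmatics:** restate the FeNO analysis in 13.4.4 as within-asthma change from day 0 on days 3 and 4. Adopt a threshold explicitly, for example two-sided p ≤ 0.025 (0.05/2). Section 13.4.2 states that rule for IL-25 and 13.4.4 extends it to the other type 2 cytokine analyses, but no within-group threshold is given for FeNO. Remove the between-cohort FeNO comparisons and the exhaled nitric oxide part of the prediction in 13.1, and add the cohort limit to 3.1, Table I and 5.1. The cost is wording in the analysis section and in those three places, and the loss of any claim that a FeNO rise is specific to asthma.

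Settling this before the FeNO data are analysed also avoids a post hoc choice between the two analyses.

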Primary Endpoint(s)	
 
1. RV-induced expression of IL-25 mRNA transcripts in the asthma and AR cohorts versus healthy controls as determined in nasal scraping samples obtained on days 3 and 4 (compared to day 0) as determined by qPCR.
 
2. RV-induced lower respiratory symptoms in the asthma cohort versus AR and healthy control as determined using modified Jackson scores (1) that will include cough, chest tightness, wheezing, and shortness of breath as well as via the asthma control test (ACT).
 
3. Severity of infection in the asthma and AR cohorts versus healthy controls as quantified by viral load present in nasal secretion samples as determined by qPCR performed on days 1, 2, 3, 4, 7.
 

Secondary Endpoint(s)	
 
1. IL-25 transcript expression in nasal scraping samples obtained on days 1, 2, and 7 (as compared to day 0).
 
2. Expression by nasal epithelial cells of a type 2 cytokine-inducing profile will be determined by also evaluating the time course of IL-33 and TSLP transcript expression by qPCR on nasal scraping samples obtained on days 0, 1, 2, 3, 4 and 7.
 
3. Expression of this type 2 cytokine-inducing profile will be corroborated by evaluating IL-25, IL-33, and TSLP protein expression by EIA on nasal secretion samples obtained via immunosorbent sponge.
 
4. Airway inflammation will be determined as increases in circulating absolute eosinophil counts, increased FeNO, and as changes in methacholine PD20.
 
5. Severity of RV infection will be corroborated as increases in upper respiratory symptoms using modified Jackson scores (1).
 

	
This scoring system includes sneezing, nasal discharge, nasal obstruction, sore throat, headache, malaise, and chills.
 
6. Severity of RV infection will be correlated with decreased innate immunity as assessed as reduced IFN-<math>\alpha</math>, -<math>\beta</math>, -<math>\lambda</math>, and IL-15 measured as qPCR of nasal scrapings and as enzyme immunoassays (EIAs) of nasal secretions (sponge-derived samples).

Accrual Objective	60 (20 each controls, AR, and asthma)
Study Duration	5 years to enroll, 8- 12 weeks for each participant to complete the study
Treatment Description	Rhinovirus (GMP RV16 HRV-16) inoculation

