#### 4.2. Inclusion Criteria

Individuals who meet all of the following criteria are eligible for enrollment as study participants. Participants in this trial will have participated in our separate (IRB protocol #12656 or 19512) screening protocol performed at day -28. Results obtained from the screening protocol will be used to initially determine eligibility as described below.

All subjects:

1. Subjects must be able to understand and provide written informed consent.
2. Age 18 to  $\leq 40$  years of age, any gender, any racial/ethnic origin
3. Female subjects of childbearing potential must have a negative pregnancy test upon study entry (day -7) and before each procedure involving pharmacologic interventions (days 0, 4, and 7).
4. Female (and male) subjects with reproductive potential, must agree to use FDA approved methods of birth control for the duration of the study such as, but not limited to, birth control pills, contraceptive foam, diaphragm, IUD, abstinence, or condoms.
5. Participants must be willing to comply with study procedures and requirements.
6. Negative test for serum neutralizing antibody to RV16 at enrollment visit ( $<1:8$ ) (Visit 1).
7. Negative CoVID-19 test within 72 hrs of RV inoculation
8. Afebrile and negative CoVID screening questions on day of RV inoculation

Allergic Rhinitis Subjects:

1. Allergy as determined by  $\geq 1$  positive prick skin test (wheal  $\geq 5$  mm diameter and 3mm larger than the diluent control) to Virginia inhalant panel within 5 years (done as part of screening protocol), and a history of symptoms of sneezing, rhinorrhea, pruritus, nasal congestion, and/or allergic conjunctivitis on natural exposure to relevant allergens.
2. Negative methacholine challenge (less than 20% decline in FEV1 at  $\leq 8$ mg/ml) within 1 year
3. FEV1  $\geq 70\%$  predicted or FEV1/FVC  $\geq 80\%$ .
4. No history of wheezing with viral infection in the last 6 years, and no use of rescue inhalers or long-term controllers for asthma in the last 6 years.

Allergic Asthmatic Subjects:

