10. Vital Signs (blood pressure, heart rate, temperature, height, weight)
11. Methacholine challenge (not to be performed if results were obtained within the past year in the separate screening protocol)
12. Between visit 1 and 2 subjects will fill out diary cards weekly.

Visit 1 can be completed in multiple visits if they occur within the visit window.

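### The three-group ANOVA of change in methacholine PD20 has no defined value for most allergic rhinitis subjects and, probably, most healthy controls, and its day -7 baseline conflicts with the rule allowing an older screening result to be reused

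*Combined protocol and SAP*

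**What the plan says.** Change in PD20 is one of three markers under secondary endpoint 4, airway inflammation (Section 3.2: "and as changes in methacholine PD20"). Section 13.4.4 says that bronchial hyperreactivity "will be quantified in terms of the changes in methacholine challenge PD20 from pre-challenge day -7 to post challenge day 4", tests by ANOVA whether the three cohorts share a mean, and then applies pairwise tests: "If rejected a Bonferroni corrected two-sided" rule at 0.05/3. Permutation methods are the fallback if the ANOVA assumptions fail. No measurement scale, top dose or non-reactor rule is given and, unlike the eosinophil paragraphs, no significance level for the global test.

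On eligibility, Section 4.2 requires of AR subjects a "Negative methacholine challenge (less than 20% decline in" FEV1 at concentrations up to 8 mg/ml, within one year. Asthmatics need at least a 20% fall at 16 mg/ml or less, from the screening protocol within the past year. No methacholine criterion is listed for healthy controls; Section 4.1 calls them non-allergic and non-asthmatic. The accrual target is "60 (20 each controls, AR, and asthma").

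On timing, Section 3.1, Table I and Section 13.4.4 all place the pre-challenge test at day -7. Section 8.2, item 11, reads "Methacholine challenge (not to be performed if results were obtained within the past year in the separate screening protocol"). The same section allows screening up to one year before Visit 1, and Visit 1 falls 5 to 28 days before inoculation. Section 4.2 places screening at day -28.

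**The concern.** The endpoint is the difference of two quantities, each of which exists only in a reactor. One cohort is selected for reacting, one for not reacting up to a stated concentration, and the third is expected mostly not to react. Whoever programs the analysis must therefore invent a value for the non-reactors, and that choice can decide the result. Section 13.1 predicts that bronchial hyperreactivity will rise only in asthmatics. A ceiling value in the other two cohorts produces that same pattern whether or not the biology does.

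The baseline is a second problem. If the pre-challenge value is a reused screening test, the change to day 4 contains whatever happened between that test and inoculation as well as the effect of the virus. Section 1.3 itself links detectable methacholine differences to challenging outside periods of allergen exposure. A test done months earlier may have been done in a different season.

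**Working it through.** The plan gives no SD, effect size or power for PD20, so there is no figure of its own to reproduce.

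**1. Who can have a value.** AR: 20 subjects, none with a 20% fall at 8 mg/ml or below at entry. Healthy: 20 subjects, non-reaction inferred from Section 4.1. Upper bound without a computable change: 20 + 20 = 40 of 60. It is a bound because an AR subject reacting between 8 and 16 mg/ml would have a value if testing goes that high.

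**2. Whether another rule supplies the value.** The detection-limit rule in Section 13.1 covers specimens below an assay limit; a PD20 above the top dose is the opposite tail. Multiple imputation in the same section is for incomplete data, whereas a non-reactor's PD20 is censored at a known dose. A permutation test still needs a number for each subject.

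**3. What happens under each possible rule.** If both non-asthmatic cohorts are set to the top dose at both visits, their changes are all exactly zero. Let m and s² be the mean and variance of change in the 20 asthmatics.
- Between-group mean square = 20 × (2/3)m² / 2 = (20/3)m².
- Within-group mean square = 19s² / 57 = s²/3.
- F = 20m²/s², the square of the asthmatics' own one-sample t statistic on 19 df.

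The nominal between-group test thus becomes a within-asthma test. It is judged against F(2, 57), whose 5% critical value is 3.16. Since √3.16 = 1.78, the true size under no change (for normal data) is P(|t19| > 1.78) = 0.092.

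A simulation with less extreme censoring agrees. Its assumptions are not from the documents: 20 per group; log2 mg/ml means 1.0, 5.5 and 6.5 for asthma, AR and healthy (2, about 45 and about 91 mg/ml); between-subject SD 1.0; within-subject SD 0.75; asthma baseline at most 16 mg/ml and the others above 8; concentration standing in for dose; 2,000 runs per setting; global ANOVA at 0.05.

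| Top | Non-reactor rule, scale | Rejects, no change | Rejects, same one-doubling worsening in all groups |
|---|---|---|---|
| 8 | top dose, log2 | 9.3% | 98% |
| 8 | top dose, raw | 9.3% | 86% |
| 16 | top dose, log2 | 8.8% | 94% |
| 16 | top dose, raw | 6.1% | 24% |

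The raw-scale rows also carry a scale effect, because equal doublings are unequal differences in mg/ml. With non-reactors dropped, at least one group has fewer than two subjects in 98.7% to 100% of runs, so the ANOVA cannot be carried out. Average numbers with both values measurable (asthma / AR / healthy) are about 18 to 19 / 0 / 0 for a top of 8 mg/ml and about 20 / 0.7 to 1.5 / 0.1 to 0.3 for 16 mg/ml.

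**4. Age of the baseline.**
- Nominal: 7 days before inoculation, 7 + 4 = 11 before the day 4 test.
- Test done at Visit 1: 5 to 28 days before inoculation, 9 to 32 before day 4.
- Reused screening result: up to 365 + 28 = 393 days before inoculation, 397 before day 4.

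Asthmatics must hold a screening result from the past year to be eligible, so Section 8.2 normally waives their Visit 1 test. The AR criterion also asks for a result within one year but does not name its source, so baseline age may differ by cohort.

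**The case against.** The strongest reply is that zero change is what the study's model predicts for AR subjects and controls, so one sentence assigning a ceiling value would complete the plan, with only 6% to 9% false rejection when nothing changes. That is fair as far as it goes: the inflation under no change is mild. It does not answer the other case. A ceiling hides real worsening in non-reactors, and the contrast between cohorts is what the three-group test is meant to show. How often this misleads depends on assumed means and SDs, so the 24% to 98% range is illustrative only.

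A second reply is that secondary objective 4 concerns the asthma cohort and that Section 13.6 already plans within-group tests for every secondary outcome. This stands. The asthma pre/post analysis remains computable, subject to the baseline problem.

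Several stronger readings are tempting and not supported:
- That exactly 40 of 60 subjects have no value. Only AR non-reaction is an entry rule, it is defined only to 8 mg/ml, and no top dose is stated.
- That baselines will typically be a year old. That is the permitted extreme; Section 4.2 puts screening at day -28.
- That regression to the mean favours the hypothesis. Asthmatics selected for a low PD20 would tend to retest higher, against it. Drift over time is the more serious concern.
- That the main analysis should be limited to tests in the 5 to 28 day window. Under the waiver this could remove nearly all asthmatics.

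**Conclusion.** The concern holds. As written, the three-group ANOVA of change in PD20 cannot be carried out validly: for most AR subjects, and probably most healthy controls, the endpoint is either undefined or fixed near zero by an unstated rule. The limit of 40 of 60 rests on inferring non-reaction in controls and on no AR subject reacting above 8 mg/ml. The baseline conflict can be read directly from the text: day -7 in Sections 3.1 and 13.4.4, a reused result up to about 393 days before inoculation under Section 8.2, and day -28 in Section 4.2. For asthmatics, reuse is the normal case.

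A reader might infer that the trial's main conclusions are at risk. They are not: PD20 is one component of one secondary endpoint, and the primary analyses and the sample size of 60 do not depend on it. The point should be settled before the data are analysed.

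**What to change.** - For the three-group comparison, replace change in PD20 with change in the methacholine dose-response slope: percent FEV1 fall at the last dose divided by cumulative dose, from the same tests. Some non-reactors will show no fall or a rise, where a plain log is undefined. Pre-specify either an offset before log transformation or a rank or permutation test on the untransformed slope.
- Keep change in log2 PD20 as a within-group analysis in the asthma cohort, with a stated rule for values above the top dose. A censored-data model across all three cohorts is a poor substitute, because with almost every AR and control value censored it barely identifies their means.
- State the top dose, whether dose or concentration is analysed, the scale, and the level of the global test.
- Reconcile Sections 3.1, 4.2, 8.2 and 13.4.4 on which test is the baseline. Report baseline age by cohort and add a sensitivity analysis by baseline age.

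The cost is SAP wording, slightly more programming, and obtaining dose-level records from the screening protocol. If those records are unavailable, slopes cannot be computed for subjects whose baseline was reused. The analysis changes need no new tests.
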